Although EGPA is a relatively rare disease, its treatment is constantly progressing, and a variety of therapeutic approaches are emerging and improving the traditional treatment model, based on the use of glucocorticoids and immunosuppressants to control the

symptoms. Glucocorticoids are the main treatment for EGPA, Cyclophosphamide is recommended as an immunosuppressant in patients who do not respond well to GC therapy or have poor prognostic factors. In patients refractory or intolerant to cyclophosphamide, rituximab, mycophenolate mofetil, and azathioprine are alternatively used. A variety of immune cells and mediators are involved in the development of diseases, and this is why drugs targeting specific immune cells or mediators are applied and help reduce the dosage of glucocorticoids to achieve better disease control on symptoms and recurrence.

Biological treatments that mainly target type 2 inflammatory pathways are widely used in clinical practice for remission induction and maintenance of EGPA: in particular, anti-interleukin 5 (IL5) strategies are an important component of treatment.

Mepolizumab 300 represents one of the treatment options for patients with EGPA. It is a humanised monoclonal antibody targeting interleukin-5 (IL-5), a cytokine involved in the activation, differentiation, and survival of eosinophils. By inhibiting IL-5 signaling, Mepolizumab significantly reduces eosinophil levels and the eosinophilic inflammation associated to EGPA.

Mepolizumab 300 is primarily used in combination with GCs for remission induction in non-severe EGPA or as an adjunct to maintain remission, with notable efficacy in reducing GC usage and improving respiratory symptoms

Mepolizumab 300 proved to be an effective treatment for eosinophilic granulomatosis with polyangiitis (EGPA) at a dose of 300 mg every 4 weeks in the multicenter, double-blind, phase III MIRRA trial (ClinicalTrials.gov NCT02020889), which demonstrated that patients treated with mepolizumab (300 mg every 4 weeks for 52 weeks) had significantly higher rates of disease remission, with a prolonged duration of remission, fewer relapses, and a reduced need for glucocorticoids, compared to those receiving a placebo.

Despite the promising results, its efficacy in patients with acute severe manifestations, including organ-threatening cardiomyopathy and gastrointestinal involvement, remains under investigation. Additionally, while the efficacy of mepolizumab in ANCA-negative EGPA has been suggested by some studies, the MIRRA trial did not show a significant association between efficacy and ANCA status.

From March 2023, Mepolizumab 300 mg administered subcutaneously every 4 weeks has been approved in Italy as adjunctive therapy for patients aged 6 years and older with relapsed/remitting or refractory eosinophilic granulomatosis with polyangiitis (EGPA).

In clinical practice, the role of the otorhinolaryngologist is crucial in assessing the evolution of symptoms and naso-sinus signs in patients with EGPA and concomitant severe and uncontrolled CRSwNP.

Studies conducted in clinical practice, or 'real-life' studies, represent a fundamental tool for assessing the effectiveness of a therapeutic treatment. Our study aims to be one of the first to investigate the efficacy on the sino-nasal region of Mepolizumab 300 mg administered subcutaneously every 4 weeks in a real-life setting, thus contributing to an improvement in knowledge on the use of this drug in the management of EGPA.

OBJECTIVES

The *primary objective* of this study is evaluating the reduction of dimension of nasal polyps measured with Nasal Polyp Endoscopic Score (NPS)

The *secondary objective* is to evaluate the improvement in nasal symptoms and quality of life in the patient measured through symptom questionnaires, the improvements in terms of smell dysfunction and symptomatology related to eosinophilic otitis media; evaluate the need of surgery or systemic corticosteroids.

ENDPOINTS

Primary endpoint

The primary endpoints will be the Improvement of NPS score (indicative of polyps score reduction) at 12 months after start of therapy.

Secondary endpoints

- Improvement of SNOT-22 score (indicative of an improvement in quality of life)
- Improvement of VAS score for nasal obstruction
- Improvement of Nasal Congestion Score (NCS)
- Improvement of VAS score for smell;
- Improvement of sniffin' sticks score;
- Evaluate adherence to drug therapy with Mepolizumab 300, any suspension of the same and reasons for discontinuing treatment (lack of efficacy, complications reported, safety profile);
- Assess how many patients require FESS surgery and/or systemic steroids for sino-nasal symptoms during treatment;
- Evaluate the improvement of symptoms of any associated comorbidities and in particular chronic eosinophilic otitis media.

Study design

Observational, retrospective/prospective, non-profit and national multicenter real-life study.

Population.

We will collect data from patients affected by EGPA and concomitant severe chronic rhinosinusitis with nasal polyps (CRSwNP) not controlled by local and systemic corticosteroids and/or surgery, who have received indication, during normal clinical practice, to therapy with Mepolizumab 300mg every 4 weeks (self-administered at home with subcutaneous autoinjector), in addition to topical nasal corticosteroids.

For the retrospective cohort, the start of observation is from 01 March 2023

We be enrolled 65 patients.

Duration of the study

The foreseen study duration is of 18 months since the approval of the present protocol by the Local Ethics Committee.

Inclusion criteria

Eligible patients will be:

- Patients over 18 years of age who can sign a written informed consent;
- Confirmed diagnosis of EGPA by rheumatologist and in treatment with Mepolizumab 300 mg every 4 weeks, according to clinical practice;
- Confirmed clinical / radiological diagnosis of chronic rhinosinusitis with diffuse naso-sinusal polyposis by nasal endoscopy and/or massive facial CT scan without contrast medium carried out within 6 months prior to the start of therapy;
- Severe disease stage, defined by Nasal Polyp Score (NPS) ≥ 5 or nasal obstruction symptom visual analogue scale (VAS) score of >5 and/or SNOT-22 ≥ 50 ;
- Inadequate symptom control with intranasal local corticosteroid therapy;
- Failure of previous medical treatments (at least 2 cycles in the last year of systemic corticosteroid) or failure of previous surgical treatment through nasal endoscopic surgery (FESS), with no clinical benefit or postoperative complications.

Exclusion criteria

- Age <18 years;
- Patients with EGPA with organ impairment or at risk of death;
- Patients undergoing radio/chemotherapy treatments for cancer in the 12 months before the start of therapy.

Procedures

All patients eligible for biological therapy will require a diagnostic work-up" according to the current guidelines (EPOS2020 and EUFOREA). According to clinical practice, patients first must have performed a CT and/or endoscopic examination to confirm the diagnosis of severe diffuse chronic rhinosinusitis with nasal polyps and allow for a staging of the disease through the application of specific and validated endoscopic scores (e.g., Nasal Polyps Score) and radiological scores (e.g., Lund Mackay score). EPOS and EUFOREA also recommend an accurate medical history collection, focusing on the main clinical features

(family history of chronic rhinosinusitis, concomitant respiratory diseases, intolerance to NSAIDs, allergies, blood hyper-eosinophilia) before starting therapy, as clinical practice.

The medical history should be sensitized by administration of questionnaires specific for nasal symptoms and quality of life and, in particular, SNOT-22 administration is largely recommended. SNOT-22 is world-wide used in common clinical practice for patients with diffuse nasal polyposis during the evaluation to the eligibility for biological therapy. It consists of two parts, one more specific for the assessment of nasal symptoms, and a second focused on the quality of life and any comorbidities associated with nasal polyps. As for the evaluation of nasal symptom (i.e. nasal obstruction, rhinorrhea, craniofacial pain, etc.) the visual analogue scale (VAS) can alternatively be used, with a score ranging from 0 to 10.

Other questionnaires widely used in clinical practice are the one on nasal congestion symptoms (NCS – Nasal congestion score) and the visual analogue scale related to the subjective loss of smell. The guidelines also recommend to routinely assess the olfactory sensitivity in a semi-objective manner. To this aim, the test currently used at national level is the subjective olfactometry using "Sniffin' Sticks", and in particular the identification test, which consists of 16 sticks filled in with odorous substances.

For the evaluation of asthma and its symptoms, the guidelines instead recommend to use of ACT (Asthma Control Test) questionnaire.

Patients receiving Mepolizumab 300 are generally evaluated in normal clinical practice at baseline and 30 days after first administration for an early re-evaluation. Subsequently, follow-up is continued with clinical re-evaluation every 3 months in the first year of treatment. Due to this reason, all participating centers will be asked to retrieve the clinical data of the visits performed at 30 days since the beginning of therapy and at 3,6,9 and 12 months.

As well, all centers will be required to provide data about any discontinuation of Mepolizumab due to adverse effects, intolerance to the drug, or related to its inefficacy. We will finally record any sino-nasal surgical treatment during treatment.

Variables

Data from the baseline clinical evaluation and follow-up visits will include a complete sensitized medical history and radiological or laboratory data carried out as normal practice.

In depth, we will collect:

- Anthropometric characteristics (age, height, gender, body mass index);
- Clinical characteristics (occupational exposure to particulate, exposure to cigarette smoke, allergies and sensitization to various allergens, presence of comorbidities, need for hospitalization for asthma and/or access to the emergency room in recent years);
- Assessment of symptoms and quality of life through validated questionnaires such as SNOT-22, Total Nasal-Symptom Score-VAS and Nasal Congestion Score (NCS);
- Nasal endoscopic staging: Nasal Polyp Score (NPS);
- Radiological extension of the CRSwNP: Lund-MacKay Score (LMS);
- Laboratory data (differential count of peripheral leukocytes, neutrophils, lymphocytes, monocytes, eosinophils, basophils), determination of total and specific IgE;
- Type of inflammation gathered from the result of non-invasive tests such as nasal cytology;
- Medications regularly taken by the patient for CRSwNP, and for comorbidities

(asthma, allergic rhinitis, etc.);

- Surgical history and any surgical treatment carried out before and during Mepolizumab therapy;
- Adverse reactions reported during drug treatment.

Sample size calculation

Based on the most recent literature, retrieved from the findings of preliminary phase III studies on Mepolizumab in the treatment of severe CRSwNP, a significant reduction NPS and SNOT-22 was observed. We therefore expect in our real-life experience a significant mean decrease at 12 months. Hence, hypothesing to assess a similar small effect size [$d = (\mu_1 - \mu_2) / \sigma$].

Considering NPS as a primary outcome a sample size of 52 patients achieves 80% power to reject the null hypothesis of zero effect size when the population effect size is 0.40 and the significance level (alpha) is 0.05. Anticipating a 20% drop-out rate, 65 patients should be enrolled to obtain the final sample size of 52 subjects. The sample size calculation was performed with a two-tailed Student's t test for paired data with PASS2025 statistical software v25.0.2.

Statistical Analysis.

The sample will be described in its clinical and demographic characteristics by descriptive statistics techniques. In depth, qualitative data will be expressed as absolute and relative percentage frequency, whilst quantitative variables by either mean and standard deviation (SD) or median and interquartile range (IQR), as appropriate. To verify the Gaussian distribution of quantitative variables, the Shapiro-Wilk test will be applied.

Fluctuations over time of NPS, NCS, VAS related to nasal obstruction, smell, sleeping disorders, rhinorrhea and craniofacial pain, nasal identification test by Sniffin' sticks, SNOT-22 questionnaire, will be assessed by repeated measurement analysis of variance or Friedman's nonparametric test, as appropriate. Correction for multiple pairwise comparisons will be performed by the Bonferroni test.

Fluctuations of the different parameters over time will be further represented by "violin plots" for quantitative variables or bar plots for qualitative/ordinal data, by using R packages "*ggpubr*", "*ggstatsplot*", "*ggplot2*", "*ggprism*" and "*ggsignif*", on both the overall sample and stratified for past surgery, asthma or ASA triad.

Potential predictors of clinical response at each time point will instead be assessed by univariable and multivariable logistic regression models with the "*rms*" R package. We will consider clinical and anamnestic variables and scores related to the immediately previous time-point (e.g., for 3-months model we will consider scores at 1-month visit).

Statistical significance will be set at a p-value <0.05 . Suggestive p values will be also reported ($0.05 \leq p < 0.10$). All analyses will be performed with R software version 4.2.0 (CRAN[®], R Core 2022, Wien, Austria).

SAFETY / REGULATORY MANAGEMENT OF ADVERSE EVENTS

Definitions for medicinal product(s)

Adverse event: any untoward medical occurrence in a patient administered a medicinal product and which does not necessarily have to have a causal relationship with this treatment.

Adverse reaction: a response to a medicinal product which is noxious and unintended. Adverse reactions may arise from use of the product within or outside the terms of the marketing authorisation or from occupational exposure. Use outside the marketing authorisation includes off-label use, overdose, misuse, abuse and medication errors.

Serious adverse reaction: any untoward medical occurrence that at any dose results in death, is life-threatening, requires inpatient hospitalisation or prolongation of existing hospitalisation, results in persistent or significant disability or incapacity, or is a congenital anomaly/birth defect.

SAFETY

Definitions

Adverse event: any untoward medical occurrence in a patient administered a medicinal product and which does not necessarily have to have a causal relationship with this treatment.

Adverse reaction: a response to a medicinal product which is noxious and unintended.

Adverse reactions may arise from use of the product within or outside the terms of the marketing authorisation or from occupational exposure. Use outside the marketing authorisation includes off-label use, overdose, misuse, abuse and medication errors.

Serious adverse reaction: any untoward medical occurrence that at any dose results in death, is life-threatening, requires inpatient hospitalisation or prolongation of existing hospitalisation, results in persistent or significant disability or incapacity, or is a congenital anomaly/birth defect or represents a new important medical event.

Regulatory management of adverse events

Any adverse event will be collected, recorded and assessed for seriousness and relatedness with study drug(s) or any other medicinal products in use, in order to identify suspected adverse reactions (ADRs).

All ADRs, regardless of the seriousness and expectedness, will be reported to National Competent Authority - AIFA, via the National Pharmacovigilance Network through the figure of Local Pharmacovigilance Responsible, as requested by the applicable law for the post-marketing pharmacovigilance activities (DM 30.04.2015 and GVP, module VI) and to the EC per local applicable rules. For the retrospective study with secondary analysis of clinical data, there is no further need of ADR reporting to national Competent Authority - AIFA, since all the reporting obligations have been fulfilled at the time of ADR presentation (DM 30.04.2015 and GVP module VI, section C 1.2.1.2.).

Ethical aspects

The study will be conducted conforming to the principals of Declaration of Helsinki. The study protocol is designed and will be conducted to ensure adherence to the principles and procedures of Good Clinical Practice and to comply with Italian laws, as described in the following documents and accepted, with their signature, by the study investigators.

REFERENCES

Firestein, Gary S., editor. | Gabriel, Sherine E., editor. | McInnes, Iain B., editor. | O'Dell, James R., editor.
Title: Kelley and Firestein's textbook of rheumatology / [edited by] Gary S. Firestein, Sherine E. Gabriel, Iain B.

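### No rule that all or consecutive eligible patients enter: charts with a known 12-month NPS can be selected into the pooled sample of 65 without trace

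*Protocol*

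**What the plan says.** Study design describes the study as "Observational, retrospective/prospective, non-profit and national multicenter real-life study". Under Population, the source of patients is "We will collect data from patients affected by EGPA and concomitant severe chronic rhinosinusitis with nasal polyps (CRSwNP", with no word such as all or consecutive. The same section dates the retrospective part ("For the retrospective cohort, the start of observation is from 01 March 2023") without closing it, and sets the total: "We be enrolled 65 patients". No section gives an order of entry, a split between retrospective and prospective patients, or a record of eligible patients not entered.

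Inclusion criteria ask for "Confirmed diagnosis of EGPA by rheumatologist and in treatment with Mepolizumab 300 mg every 4 weeks, according to clinical practice", so a patient may enter well after the first dose. Under Procedures, "all participating centers will be asked to retrieve the clinical data of the visits performed at 30 days since the beginning of therapy" and at 3, 6, 9 and 12 months. The primary endpoint is NPS improvement at 12 months after the start of therapy. Under Duration of the study, "The foreseen study duration is of 18 months since the approval of the present protocol by the Local Ethics Committee".

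The Sample size calculation section treats the study as one sample: 52 evaluable patients for an effect size of 0.40, raised to 65 for 20% drop-out.

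**The concern.** For a patient who began treatment at least 12 months before entry, the chart can already hold the 12-month NPS. Whoever decides on entry can see it, and can also see whether the record is complete. A centre could obey every written rule and still submit mainly its better responders or its tidiest charts. Preferring complete charts needs no bad intent, and it biases the result to the extent that well-documented patients did better.

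The estimate is an uncontrolled before-after change, so no comparison arm would share the distortion and reveal it. Without a log, the charts left out leave no trace, and no later analysis can recover them. Who enters is a matter for the protocol and cannot be repaired in an analysis plan.

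**Working it through.** **1. The plan's own figure.** Inputs from Sample size calculation: effect size 0.40, two-sided alpha 0.05, 80% power, paired t test, 20% drop-out. With exact noncentral-t power, n = 51 gives 0.7999 and n = 52 gives 0.808, so 52 is correct. Then 52/(1 − 0.20) = 65. The arithmetic of the sample size is sound.

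**2. Room for prospective patients.** 18 months of study less 12 months of follow-up leaves 6 months. At most, patients starting in about the first 6 months can be followed from first dose to the primary endpoint. The retrospective share may therefore be large, but the protocol does not state it.

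**3. Model for selection.** Assumptions, none of them from the protocol:
- Change scores are standard normal, with true mean zero. NPS is an ordinal score, so this is an approximation.
- Exactly the worst share q of retrospective charts is omitted.
- Prospective patients are unselected.
- A share f of the analysed sample is retrospective.

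For the retrospective part, with z the q-quantile of the standard normal:
- mean m = φ(z)/(1 − q)
- variance v = 1 + z·m − m²

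| q | z | m | SD = √v |
|---|---|---|---|
| 5% | −1.645 | 0.109 | 0.900 |
| 10% | −1.282 | 0.195 | 0.844 |
| 20% | −0.842 | 0.350 | 0.764 |

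For the pooled sample:
- mean = f·m
- variance = f(v + m²) + (1 − f) − (f·m)²
- apparent d = mean/√variance

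Example with f = 0.5 and q = 20%: the mean is 0.175. The variance is 0.5 × (0.583 + 0.1225) + 0.5 − 0.0306 = 0.822, so the SD is 0.907 and d = 0.175/0.907 = 0.19.

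Apparent d with no true change:

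| Retrospective share | worst 5% omitted | worst 10% | worst 20% |
|---|---|---|---|
| 25% | 0.03 | 0.05 | 0.09 |
| 50% | 0.06 | 0.10 | 0.19 |
| 75% | 0.09 | 0.16 | 0.31 |
| 100% | 0.12 | 0.23 | 0.46 |

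The entry for 50% and 10% is 0.105 before rounding.

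**4. Chance of a significant result with no true change.** This comes from 20,000 simulated studies of 52 analysed patients, with a two-sided t test at 0.05 and omissions rounded to whole charts:

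| Retrospective share | worst 10% omitted | worst 20% |
|---|---|---|
| 25% | 6% | 9% |
| 50% | 12% | 25% |
| 75% | 20% | 59% |
| 100% | 39% | 85% |

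With no omission the rate stays near 5% (4.7% to 5.4%).

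**5. What such selection would need.** If all 65 were retrospective, omitting 5%, 10% or 20% requires 65/0.95 = 68.4, 65/0.90 = 72.2 or 65/0.80 = 81.3 eligible charts. The protocol does not give the number of eligible patients.

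**The case against.** The strongest reply is that nothing shows selection will happen and that there may be little room for it. The protocol calls EGPA relatively rare, and Population adds severe uncontrolled polyposis. If there are few more than 65 eligible, consenting patients, there is little to choose from. This stands as a limit on the likely size. It does not close the gap, because the number of eligible patients is not stated and no log would show it afterwards.

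The protocol also asks centres for data on discontinuation. That helps for patients who were entered, but says nothing about eligible patients who were not.

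Some stronger readings are tempting and are not supported:
- **That 65 is a quota per centre.** It is the study-wide sample size, and no centre allocation is stated.
- **That the planned analysis strata wrongly omit data source.** The phrase "on both the overall sample and stratified for past surgery, asthma or ASA triad" belongs to the sentence on violin and bar plots and does not define the primary analysis. A breakdown by cohort may also be left to an analysis plan that is not shown.
- **That the treating otorhinolaryngologist chooses who enters.** The protocol does not say who decides.
- **That prospective patients are a clean internal check.** Patients may enter while already on treatment. Someone entered at month 11 has a 12-month visit still to come but may have a 9-month NPS on file.

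**Conclusion.** The concern holds as a gap in the entry rules. The protocol permits patients to be chosen with the primary outcome known, and keeps no record that would reveal it. It contains no evidence that this occurs, and its sample size arithmetic is correct.

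A reader might infer that selection alone could produce the planned effect, since 0.46 exceeds 0.40. That needs a wholly retrospective sample and perfect omission of the worst fifth. At a 25% or 50% retrospective share the same omission gives less than half the planned effect. The share and the selection rate are both assumptions, so the tables show a range of possible bias and are not an estimate of it. If the drug does reduce polyps, selecting better outcomes would still overstate by how much, and that estimate is the study's main result. The change should be made before patients are entered.

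**What to change.** Add to Population wording such as:

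> *Each centre invites every eligible patient whose first 300 mg dose fell between 01 March 2023 and [closing date], in order of first dose, whatever the outcome or the completeness of the chart, and keeps a log of eligible patients not entered, with the reason.*

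Treat 65 as a minimum, and complete the window rather than stopping part-way through a centre's list. A stated closing date is essential, because without one the list never ends and the rule cannot be applied.

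As a secondary check, report the 12-month NPS change separately for patients entered at or before their first dose and for those entered later. The first group may be small, given the roughly 6 months available for new starts, so this is descriptive support and not a test.

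The cost is a short log per centre, some incomplete charts in the data set, and a total that may exceed 65. The 52 evaluable patients required do not change, and no clinical procedure is affected.

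### The treatment criterion is not tied to the start of therapy, so read as written it leaves out retrospective patients who stopped mepolizumab before enrolment

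*Protocol*

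**What the plan says.** The Study design section calls the study "Observational, retrospective/prospective, non-profit and national multicenter real-life study". The Population section adds: "For the retrospective cohort, the start of observation is from 01 March 2023". It describes the patients as those "who have received indication, during normal clinical practice, to therapy with Mepolizumab 300mg every 4 weeks".

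A single list under Inclusion criteria serves both parts. Its second item asks for a rheumatologist's diagnosis of EGPA and for the patient to be "in treatment with Mepolizumab 300 mg every 4 weeks, according to clinical practice". Its first item admits "Patients over 18 years of age who can sign a written informed consent". Neither item names a date or event at which it is to be judged, and there is no separate rule for retrospective patients.

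The primary endpoint is "Improvement of NPS score (indicative of polyps score reduction) at 12 months after start of therapy". One secondary endpoint covers adherence, "any suspension of the same and reasons for discontinuing treatment", and lists lack of efficacy first among those reasons. The Procedures section requires every centre to supply data on discontinuation for adverse effects, intolerance or inefficacy.

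**The concern.** Eligibility should be settled by what is known when therapy starts. Here it can depend on a status observed later, possibly after the outcome itself. A patient who started in 2023, did not respond and stopped would not be in treatment when a centre compiles its list. That patient would be missing from the NPS analysis and also from the count of discontinuations.

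This is prevalent-user selection. The study has no control group that would reveal it. Patients whose charts are never entered cannot be recovered by any later analysis, so a statistical analysis plan cannot repair it.

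**Working it through.** **1. The passages side by side.**

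- Population: having received the indication is enough; current status plays no part.
- Inclusion criteria: the patient must be in treatment.
- Secondary endpoints and Procedures: discontinuations and their reasons are to be collected. This duty concerns enrolled patients and cannot make an ineligible patient eligible.
- Time anchors: the endoscopy/CT criterion and the cancer-treatment exclusion both refer explicitly to the start of therapy. The treatment criterion does not.

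**2. Timing.** The protocol cites a 2025 publication and a 2025 release of its sample size software, so it dates from 2025 or later. A patient who started in March 2023 reached 12 months in March 2024. For such patients the criterion is applied after the primary endpoint has been reached. The study lasts 18 months from approval, so a new starter who is to reach 12 months has about 18 − 12 = 6 months in which to enter. Much of the sample may therefore be retrospective, but the split is not stated.

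**3. The plan's own figure.** With a two-sided paired t test, effect size 0.40 and alpha 0.05, the noncentral t distribution gives power 0.7999 at n = 51 and 0.808 at n = 52. So 52 is the smallest n with at least 80% power. With 20% drop-out, 52 / 0.8 = 65. Both figures reproduce.

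**4. Illustration of the bias.** The protocol gives none of the following inputs, so all are assumptions:

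- q: share of starters who stopped before enrolment and are excluded
- k: mean NPS change in stoppers as a fraction of that in continuers
- r: share of the analysed cohort that is retrospective

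The mean over all starters is [(1 − q) + qk] times the mean in continuers. If prospective stoppers are kept in the analysis, the relative overstatement is

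r × {1 / [(1 − q) + qk] − 1}.

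| q | k = 0, r = 1 | k = 0.5, r = 1 | k = 0, r = 0.5 | k = 0.5, r = 0.5 |
|---|---|---|---|---|
| 10% | 1/0.90 − 1 = 11% | 1/0.95 − 1 = 5.3% | 5.6% | 2.6% |
| 20% | 1/0.80 − 1 = 25% | 1/0.90 − 1 = 11% | 12.5% | 5.6% |
| 30% | 1/0.70 − 1 = 43% | 1/0.85 − 1 = 18% | 21% | 8.8% |

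On the effect-size scale, take a true value of 0.40 over all starters, k = 0, r = 1 and a constant SD. The selected cohort would show 0.40/0.9 = 0.44, 0.40/0.8 = 0.50 and 0.40/0.7 = 0.57.

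**The case against.** The best counter-argument is that the phrase only names the drug and regimen, and that the authors meant patients who started it. The context supports this: other criteria are anchored at the start of therapy, the severity thresholds make sense only at baseline, the Population paragraph speaks of an indication, and stopping is an endpoint. The reading is plausible, but the criterion does not say it. Centres could apply the words differently, and the literal reading removes exactly the patients the endpoint needs.

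Other parts of the case against do stand, and they limit what can be claimed:

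- A reader might take the protocol's 20% as the stopping rate and conclude that the effect is overstated by 25%. The 20% is anticipated study drop-out. The 25% also needs zero change in every stopper and an entirely retrospective cohort. Patients who stop for adverse effects may have improved.
- A reader might infer that observed discontinuation in the retrospective part would be about 0%. Only permanent stops before enrolment are lost. Temporary suspensions stay visible, and a patient enrolled within the first 12 months who stops later is counted.
- A reader might infer that a drop-out allowance is meaningless in such a cohort. It can cover later losses and charts without a 12-month NPS. It does not correct selection before enrolment.
- The consent criterion might suggest that deaths are a major route of exclusion. The protocol gives no count of deaths, it already excludes patients at risk of death, and the consent documents are not in the text at hand. This route is probably minor.
- Recording only a stopping date would improve the discontinuation count but would not bring stoppers into a paired NPS comparison. The remedy must therefore also cover their NPS data.

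**Conclusion.** The criterion is fixed badly and contradicts the protocol's own population statement and discontinuation endpoint. The effect is confined to the retrospective part, because stops after enrolment are still captured. The direction, more favourable NPS change and fewer discontinuations, is an inference: it rests on stoppers doing worse on average than continuers. Lack of efficacy being a listed reason for stopping makes that likely but does not prove it.

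The size cannot be computed from the protocol. The tabulated range, about 5% to 43% for an all-retrospective cohort with 10% to 30% excluded, shows what could happen and is not an estimate. The sample size of 52 evaluable and 65 enrolled is not in dispute.

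**What to change.** Reword the treatment criterion along these lines: *started mepolizumab 300 mg every 4 weeks on or after 01 March 2023 (first dose = time zero), whether or not still on treatment*. In addition:

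- Have each centre enter all consecutive eligible starters.
- Collect the available NPS through 12 months regardless of discontinuation, with the stopping date and reason.
- Include stoppers in the primary analysis, with a sensitivity analysis for those without a 12-month NPS, for example assuming no change.
- Report per centre how many starters were not included and why, including those who could not give consent.

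The cost is a change to one criterion, a few more charts per centre and a possibly less favourable estimate. The change has to be made before centres compile their retrospective lists.
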